4.2.2. Adherence to Study Drug

The total number of tablets administered will be summarized using descriptive statistics (n, mean, SD, median, Q1, Q3, minimum, and maximum).

The presumed total number of tablets administered to a subject will be determined by the data collected on the drug accountability CRF using the following formula:

$$\begin{aligned} \text{Total Number of Doses Administered} = \\ (\sum \text{No. of Tablets Dispensed}) - (\sum \text{No. of Tablets Returned}) \end{aligned}$$

The level of adherence to the study drug regimen will be assessed based on the total amount of study drug administered relative to the total amount of study drug prescribed at baseline.

The level of adherence will be expressed in percentage using the following formula:

$$\text{Level of Adherence (\%)} = \left(\frac{\text{Total Amount of Study Drug Administered}}{\text{Total Amount of Study Drug Prescribed at Baseline}} \right) \times 100$$

Note: If calculated adherence is greater than 100%, the result will be set to 100%.

In this study, the total amount of SOF/VEL (400 mg/100 mg) prescribed for 12 and 24 weeks would require 84 and 168 tablets, respectively; weight-based RBV (200 mg) prescribed for 12 and 24 weeks would require 252 / 504 (3 tablets/day for baseline weight \leq 60 kg) , 336 / 672 (4 tablets/day for baseline weight $>$ 60 kg to \leq 80 kg) tablets, or 420 / 840 (5 tablets/day for baseline weight $>$ 80 kg), respectively.

Subjects who prematurely discontinue study drug due to lack of efficacy (ie, virologic failure) will have the total amount of study drug prescribed calculated up to the first date that virologic failure criteria were met. For virologic failure confirmed by 2 consecutive measurements, the date of the first measurement will be used. If there were study drug bottles dispensed on or after the date that the subject first met virologic failure criteria, these bottles will not be included in the calculation of adherence. If a bottle was dispensed and the bottle was returned empty, then the number of tablets returned will be entered as zero. If a bottle was dispensed but not returned (missing), the number of tablets taken from that bottle will be counted as zero.

Descriptive statistics for the level of adherence (n, mean, SD, median, Q1, Q3, minimum, and maximum) with the number and percentage of subjects belonging to adherence categories (eg, $<$ 80%, \geq 80 to $<$ 90%, \geq 90%) will be provided by treatment group and total for the Safety Analysis Set. Categorical displays will be provided for the number of subjects who were at least 80% adherent to their study drug regimen (ie, adherence was \geq 80% for each of the study drugs). No inferential statistics will be provided.

No inferential statistics will be provided for duration of exposure and adherence to study drug.

A separate by-subject listing of study drug administration and drug accountability will be provided by subject ID number (in ascending order) and visit (in chronological order).

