3.4.1. Virologic Response-Based Treatment Stopping Criteria

The following on-treatment Virologic Response-based Treatment Stopping Criteria will be utilized:

- Confirmed HCV RNA \geq LLOQ after 2 consecutive HCV RNA $<$ LLOQ
- Confirmed $> 1 \log_{10}$ increase in HCV RNA from nadir
- HCV RNA \geq LLOQ through 8 weeks of treatment

Confirmation should be performed as soon as possible and must occur no later than 2 weeks after an initial observation indicating virologic failure during the on-treatment phase.

[figure not shown]
Subjects who terminate study drugs early due to virologic failure as defined above will complete the Early Termination (ET) visit and all posttreatment visits.

PPD

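### For subjects who stop for virologic failure, SAP 4.2.2 ends prescribed drug at the first failing HCV RNA but still counts later tablets from the bottle in use, which can lift a score above 80% (minor)

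*SAP*

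**What the plan says.** SAP 4.2.2 defines adherence as study drug administered divided by study drug prescribed at baseline.

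- **Numerator.** "The presumed total number of tablets administered to a subject will be determined by the data collected on the drug accountability CRF", as the sum dispensed minus the sum returned. No calendar date limits it.
- **Denominator.** Normally this is the full course. For subjects who stop early for virologic failure it is the "total amount of study drug prescribed calculated up to the first date that virologic failure criteria were met".
- **Date used.** "For virologic failure confirmed by 2 consecutive measurements, the date of the first measurement will be used".
- **Bottle exclusion.** The only date-based limit on the numerator reads: "study drug bottles dispensed on or after the date that the subject first met virologic failure criteria, these bottles will not be included".
- **Cap.** "If calculated adherence is greater than 100%, the result will be set to 100" percent.
- **Missing bottle.** If a bottle is not returned, "the number of tablets taken from that bottle will be counted as zero".

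Protocol 3.4.1 requires breakthrough and rebound to be confirmed, and confirmation "must occur no later than 2 weeks after an initial observation indicating virologic failure during the on-treatment phase". Protocol 5.5 requires a pill count at every visit after Day 1.

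SAP 3.4 lists adherence below 80% versus 80% or more as an SVR12 subgroup. SAP 4.2.2 counts a subject as adherent only if the score is at least 80% on each study drug.

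**The concern.** The SAP sets out to align the two sides, since it shortens the denominator and drops later bottles. It overlooks the bottle in use on the day of the first failing sample. That bottle counts in full, including tablets taken after the denominator has stopped.

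The mismatch can only raise a score, and it applies only to subjects who failed on treatment. In that group, poor adherence is the natural rival to drug failure as an explanation. A poor adherer who failed can be displayed as adherent. Moving such a subject across the cut-off lowers SVR12 in the 80%-or-more subgroup and removes a failure from the other. The cap also removes the one sign, a ratio above 100%, that would reveal the problem.

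**Working it through.** **Check of the plan's own figures.** Prescribed amount = days × units per day. For SOF/VEL, 84 × 1 = 84 and 168 × 1 = 168. For RBV at 3, 4 and 5 capsules a day, the amounts are 252/504, 336/672 and 420/840. All match SAP 4.2.2.

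**Inputs.**
- F = study day of the first failing sample (7 × week).
- L = days from that sample to stopping. The ceiling for confirmation is 14 (Protocol 3.4.1); 7 is assumed as a shorter case.
- SOF/VEL bottles hold 28 tablets (Protocol 5.2.2), taken as one bottle per 28 days.
- Dispensing is at Day 1 and Weeks 4 and 8, plus Weeks 12, 16 and 20 in the 24-week group (Protocol 6.2.1, 6.3 and Appendix 2). HCV RNA is also measured at Weeks 1, 2, 3, 5, 6 and 10, when nothing is dispensed.
- a = true adherence, assumed constant. The subject is assumed to move to each new bottle when it is dispensed.

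**Formula.** Let S = 28 × number of bottles dispensed before day F. Dosing days whose tablets are counted: N = min(F + L, S). SAP score = min(100%, a × N/F). True adherence that scores exactly 80%: a* = 80% × F/N.

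| First failing sample | F | S | N, L = 7 | a*, L = 7 | N, L = 14 | a*, L = 14 |
|---|---|---|---|---|---|---|
| Week 2 | 14 | 28 | 21 | 53.3% | 28 | 40.0% |
| Week 3 | 21 | 28 | 28 | 60.0% | 28 | 60.0% |
| Week 4 | 28 | 28 | 28 | 80.0% | 28 | 80.0% |
| Week 5 | 35 | 56 | 42 | 66.7% | 49 | 57.1% |
| Week 6 | 42 | 56 | 49 | 68.6% | 56 | 60.0% |
| Week 8 | 56 | 56 | 56 | 80.0% | 56 | 80.0% |
| Week 10 | 70 | 84 | 77 | 72.7% | 84 | 66.7% |

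Weeks 12, 16 and 20 in the 24-week group also give 80.0%, because the newly dispensed bottle is excluded. In the 12-week group, 14 days after Week 10 is Day 84, the planned end of treatment. The rule for premature stops would then not apply, so the 14-day Week 10 figure belongs to the 24-week group.

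**Which visits are realistic.** Breakthrough under Protocol 3.4.1 needs two consecutive results below LLOQ first, so on scheduled visits it cannot appear before Week 3. Rebound at Week 1 would need a rise of more than 1 log10 above the Day 1 value, so Week 1 is effectively excluded. Week 2 is open only to rebound. Nonresponse is met at Week 8, a dispensing visit.

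**Whole-tablet example, Week 6.** The subject takes 25 of 42 SOF/VEL tablets by Day 42, then 9 of the next 14, and stops on Day 56. Two bottles (56 tablets) were dispensed and 22 tablets returned, so 56 − 22 = 34 are counted.
- True adherence: 25/42 = 59.5% to Day 42, and 34/56 = 60.7% to Day 56.
- SAP score: 34/42 = 81.0%.
- RBV at 3 capsules a day in the same pattern: 75 + 27 = 102 counted, and 102/126 = 81.0%. The subject passes on both drugs, provided RBV is supplied in step with SOF/VEL.

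**The case against.** Several points on the other side stand.

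- **Size.** Two weeks is a ceiling; Protocol 3.4.1 asks for confirmation as soon as possible. At 7 days the effect at Weeks 5, 6 and 10 is smaller, though it remains.
- **Both drugs.** A subject must reach 80% on SOF/VEL and on RBV. RBV is scored against the baseline prescription, so a reduction or stop lowers its score. RBV also comes in 140-capsule packs (Protocol 5.3.2), so its inflation depends on how packs are issued. The rule counting an unreturned bottle as zero also pulls scores down.
- **Frequency.** In the protocol's ASTRAL-1 summary the only two virologic failures were relapses, and ASTRAL-2 had none on SOF/VEL. This is indicative only: in ASTRAL-2 just 14.7% of subjects were treatment experienced, whereas everyone here has failed a DAA regimen.
- **Use.** Adherence carries no inferential statistics, and a by-subject, by-visit accountability listing is planned. A reader could check the dosing there, but the listing does not correct the score.

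A reader might infer that the Week 3 limit is 48%, from 80% × 21/35. That requires the subject to keep using the old bottle after Week 4. If the subject moves to the new bottle, which the SAP excludes, only 28 days count and the limit is 60%.

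A reader might also infer that the rule makes adherence look irrelevant to SVR12. The documents give neither the size of the below-80% subgroup nor the number of on-treatment failures, so they do not support a claim that strong.

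**Conclusion.** The rule is wrong as written, and the matter is minor. For confirmed breakthrough or rebound first seen at a visit without dispensing (realistically Weeks 2, 3, 5, 6, 10 or unscheduled), numerator and denominator cover different periods. True adherence of roughly 57% to 73% at Weeks 5 to 10 can score 80%, depending on a lag of 7 to 14 days. These figures rest on constant adherence, one 28-tablet bottle per 28 days and a move to each new bottle when dispensed.

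It would be a mistake to read this as affecting all virologic failures or the trial's main result. Relapsers and subjects who stop for other reasons are outside the rule. Failures first seen at dispensing visits, including nonresponse at Week 8, are essentially unaffected. The exception is use of leftover tablets: at Week 8, 60% true adherence with 14 more days on old bottles would score 0.60 × 70/56 = 75%. The primary SVR12 test does not use adherence.

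What remains is that a non-adherent on-treatment failure can be placed in the wrong SVR12 subgroup.

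**What to change.** In SAP 4.2.2, make both sides cover the same period for subjects who stop for virologic failure. Either version works.

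1. **Stop at the first failing sample.** Keep the denominator as it is. Count tablets only up to the pill count at that visit, as tablets dispensed before it minus tablets on hand. In the example the score becomes 25/42 = 59.5%. If the sample was taken between counts, use the nearest count and end the prescribed amount on the same date.
2. **Run to the last dose.** End the prescribed amount at the last dose date already derived in SAP 3.8.1, and drop the bottle exclusion. In the example the score becomes 34/56 = 60.7%.

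The cost is a sentence or two in the SAP and a small programming change. Version 1 uses counts that Protocol 5.5 already requires. The documents do not say that each visit's count is held in the database, so a few may have to be entered from source. Version 2 avoids that, but its score includes dosing after the first failing sample.

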4.3. Protocol Deviations

A summary of important protocol deviations will be provided by the Gilead Clinical Operations group for subjects in the Safety Analysis Set.

Subjects who received study drug other than their randomized treatment assignment will be listed with the start and stop dates that they received incorrect study drug.

5. BASELINE CHARACTERISTICS

5.1. Demographics

Subject demographic variables (ie, age, sex, race, and ethnicity) will be summarized by treatment group, genotype (1, 2, and total), and total using descriptive statistics (n, mean, SD, median, Q1, Q3, minimum, and maximum) for age, and using the numbers and percentages of subjects for age categories (< 65 years, \geq 65 years), sex, race, and ethnicity. Age is calculated in years at the date of initial study drug administration. If a subject did not receive study drug after randomization, the subject's age will be calculated from the date that the subject signed the informed consent form. The summary of demographic data will be provided for the Safety Analysis Set.

A by-subject demographic listing, which includes the date the informed consent was signed, will be provided by subject ID number in ascending order.

5.2. Other Baseline Characteristics

Other baseline characteristics include:

- body mass index (BMI; in kg/m²) as a continuous variable and as categories (< 25 kg/m², \geq 25 kg/m²)
- HCV genotype/subtype (1 [further broken down to 1a, 1b, and 1 other if applicable], 2 [further broken down to 2a, 2b, and 2 other if applicable])
- Number of prior DAAs (1, 2, 3, >3)
- Number of prior HCV treatment regimens (1, 2, 3, 4, 5, >5)
- Prior DAAs (NS5A only, NS5A + NS5B, NS5A + NS3, NS5A + NS5B + NS3, NS5B only, NS5B + NS3)
- cirrhosis (cirrhosis, absence of cirrhosis, missing)
- IL28B (CC, non-CC; with non-CC further broken down to CT, TT)
- baseline HCV RNA (\log_{10} IU/mL) as a continuous variable and as categories (< 800,000 IU/mL, \geq 800,000 IU/mL, and < 5 \log_{10} IU/mL, \geq 5 \log_{10} IU/mL)
- baseline ALT (U/L) as a continuous variable and as categories (\leq 1.5 \times ULN, > 1.5 \times ULN)
- most recent prior HCV treatment response (non-responder, relapse/breakthrough, early treatment discontinuation, met a virologic stopping rule not otherwise listed, or unknown)
- estimated glomerular filtration rate (eGFR) using the Cockcroft-Gault equation

eGFR will be calculated by the Cockcroft-Gault method: $eGFR_{CG} \text{ (mL/min)} = [(140 - \text{age (yrs)}) \times \text{weight (kg)} \times (0.85 \text{ if female})] / (\text{serum creatinine (mg/dL)} \times 72)$, where weight is total body mass in kilograms.

These baseline characteristics will be summarized by treatment group, genotype (1, 2, and total), and total using descriptive statistics (n, mean, SD, median, Q1, Q3, minimum, and maximum) for continuous variables and using the numbers and percentages of subjects for categorical variables. The summary of baseline characteristics will be provided for the Safety Analysis Set.

A by-subject listing of other baseline characteristics will be provided by subject ID number in ascending order.

A separate by-subject data listing for cirrhosis determination and prior HCV treatment and response will be provided for all subjects at screening.

5.3. Medical History

General medical history data will not be coded, but will be listed only.

A by-subject listing of disease-specific medical history will be provided by subject ID number in ascending order.

6. EFFICACY ANALYSES

6.1. Primary Efficacy Endpoint

6.1.1. Definition of the Primary Efficacy Endpoint

The primary efficacy endpoint is the proportion of subjects with SVR12, defined as HCV RNA < LLOQ (ie, < 15 IU/mL) 12 weeks after cessation of treatment. The primary analysis will be performed after all randomized subjects have been followed through 12 weeks posttreatment or discontinued from study. The COBAS® AmpliPrep/COBAS® TaqMan® HCV Quantitative Test, v2.0 will be used to measure HCV RNA.

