5.6. Prior and Concomitant Medications

Concomitant medications taken within 30 days prior to Screening, up to and including 30 days after the last dose of study drugs need to be recorded in the source documents and eCRFs.

The following medications are prohibited from **28 days prior to the Day 1 visit** through the end of treatment:

- Investigational agents or devices for any indication
- Drugs disallowed per prescribing information for RBV

Concomitant use of certain medications or herbal/natural supplements (such as substrates, inhibitors or inducers of drug transporters or metabolizing enzymes, eg, P-gp or CYP3A) with the study drugs may result in pharmacokinetic interactions resulting in increases or decreases in exposure of the study drugs or these medications.

[Table 5-2](#) below contains medications that are prohibited from **21 days prior to Day 1** through the end of treatment and those medications that may be used with caution. The use of amiodarone is prohibited from **60 days prior to Day 1** through the end of treatment.

Table 5-2. Disallowed and Concomitant Medications to be Used with Caution

Drug Class	Agents Disallowed	Use with Caution
Acid Reducing Agents ^a		Proton- Pump Inhibitors, H2-Receptor Antagonists, Antacids
Anticonvulsants ^b	Phenytoin, Carbamazepine, Phenobarbital, Oxcarbazepine ^g	
Antimycobacterials ^b	Rifampicin, Rifabutin, Rifapentine ^g	
Cardiac Medications ^c	Amiodarone ^d	Diltiazem, Verapamil, Dronedarone ^g , Quinidine, Ranolazine ^g , Bosentan, Olmesartan, Valsartan, Digoxin ^e
Herbal/Natural Supplements ^b	St. John's Wort, Echinacea, Milk thistle (i.e., silymarin), Chinese herb sho-saiko-to (or Xiao-Shai-Hu-Tang)	
HMG-CoA Reductase Inhibitors ^f		Rosuvastatin (≤ 10 mg/day)
Other	Modafinil ^b , Sulfasalazine ^{c, g} , Methotrexate ^c	

a Proton pump inhibitor (PPI) doses comparable with omeprazole 20 mg can be administered with SOF/VEL when SOF/VEL is administered with food. H2-receptor antagonists must not exceed a dose of 40 mg famotidine or equivalent and can be taken simultaneously with SOF/VEL and/or staggered by 12 hours. Antacids that directly neutralize stomach acid may not be taken within 4 hours (before or after) of SOF/VEL administration.

b May result in a decrease in the concentration of study drugs.

c May result in an increase in the concentration of study drugs and/or concomitant medications

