6.4. Posttreatment Assessments (± 5 days)

The posttreatment Week 4, 12, and 24 visits should be timed from the date of last administration of any study drugs for all subjects, regardless of whether they are a virologic failure or discontinued study drugs early.

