6.6. Unscheduled Visit

A subject should attend an unscheduled visit if requested by the sponsor or the investigator. The assessments are at the investigator's discretion as clinically indicated, but the investigator should, at a minimum, collect AE and concomitant medication information. At all unscheduled visits initiated for the purpose of confirming virologic failure, a sample for a viral RNA sequencing/phenotyping must be collected.

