Appendix 2. Study Procedures Table

	Screening	Day 1 ^a	Treatment Week (±3 days)												ET ^c	Posttreatment Week (±5 days)		
			1	2	3	4	5	6	8	10	12	16 ^b	20 ^b	24 ^b		4	12	24
Clinical Assessments																		
Informed Consent	X																	
Determine Eligibility	X	X																
Medical History	X																	
Physical Examination	X	X	X	X	X	X	X	X	X	X	X	X	X	X	X	X	X	X
Height	X																	
Weight	X	X	X	X	X	X	X	X	X	X	X	X	X	X	X	X	X	X
Vital Signs ^d	X	X	X	X	X	X	X	X	X	X	X	X	X	X	X	X	X	X
12-lead ECG ^e	X																	
Adverse Events and Concomitant Medications ^f	X	X	X	X	X	X	X	X	X	X	X	X	X	X	X	X		
Pregnancy Prevention Counseling		X									X				X	X	X	X
Health Related Quality of Life ^g		X									X				X	X		X
Imaging for HCC ^h	X																	
Review of Study Drug Adherence and Drug Accountability ⁱ			X	X	X	X	X	X	X	X	X	X	X	X	X	X		
Study Drug Dispensing ^j		X				X			X			X ^b	X	X				
Laboratory Assessments																		
Hematology & Chemistry	X	X	X	X	X	X	X	X	X	X	X	X	X	X	X	X	X	
Coagulation (PT, aPTT and INR)	X	X	X	X	X	X	X	X	X	X	X	X	X	X	X	X		
HCV RNA (Plasma)	X	X	X	X	X	X	X	X	X	X	X	X	X	X	X	X	X	X

	Screening	Day 1 ^a	Treatment Week (±3 days)												ET ^c	Posttreatment Week (±5 days)		
			1	2	3	4	5	6	8	10	12	16 ^b	20 ^b	24 ^b		4	12	24
Viral RNA Sequencing /Phenotyping and/or HBV DNA Sample (Plasma)		X	X	X	X	X	X	X	X	X	X	X	X	X	X	X	X	X
Single PK			X	X	X	X	X	X	X	X	X	X	X	X				
Intensive PK Substudy Collection ^k				X	X	X												
Serum or Urine Pregnancy Test ^l	X	X				X			X		X	X	X	X	X	X	X	X
Urinalysis	X																	
HCV Genotype, IL28B Genotype	X																	
HCV Ab, HIV Ab, HBsAg, HBsAb, HBcAb	X																	
HbA1c	X																	
FibroTest [®]	X																	
Archive plasma sample ^m		X									X			X	X			
Single Genomic Sample ⁿ		X																

a Day 1 assessments must be performed prior to dosing.

b Only to be completed for subjects on the 24 week treatment regimen

c ET = Early Termination.

d Vital signs include resting blood pressure, pulse, respiratory rate and temperature.

e Subjects will be required to rest in a supine position for ≥ 5 minutes prior to making a recording. The investigator (or qualified designee) should review the ECG traces recorded in real time for clinically significant abnormalities.

f Adverse events and Concomitant Medications will be collected up to 30 days after the last dose of all study drugs.

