6.2. Secondary Efficacy Endpoints

6.2.1. Definition of Secondary Efficacy Endpoints

Secondary efficacy endpoints include the following:

- The proportion of subjects who attain SVR at 4 and 24 weeks after cessation of treatment (SVR4 and SVR24)
- The percentage of subjects with HCV RNA < LLOQ while on treatment by study visit
- HCV RNA (\log_{10} IU/mL) and change from baseline in HCV RNA (\log_{10} IU/mL) through end of treatment (EOT)
- The percentage of subjects with virologic failure as the following:
 - On-treatment virologic failure
 - HCV RNA \geq LLOQ after having previously had HCV RNA < LLOQ, while on treatment, confirmed by 2 consecutive values (Note: second confirmation value may be posttreatment) or last available on-treatment measurement with no subsequent follow-up values (ie, breakthrough)
 - $> 1 \log_{10}$ IU/mL increase in HCV RNA from nadir while on treatment, confirmed by 2 consecutive values (Note: second confirmation value may be posttreatment) or last available on-treatment measurement with no subsequent follow-up values (ie, rebound)
 - HCV RNA persistently \geq LLOQ through 8 weeks of treatment (ie, nonresponse)
 - Relapse
 - HCV RNA \geq LLOQ during the posttreatment period having achieved HCV RNA < LLOQ at EOT, confirmed by 2 consecutive values or last available posttreatment measurement
- Characterization of HCV drug resistance substitutions at baseline, during, and after therapy with SOF/VEL+RBV

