6.2.2. Analysis Methods for Secondary Efficacy Endpoints

For analyses of HCV RNA < LLOQ by visit while on treatment and during the posttreatment (SVR) follow-up period, subjects will be assigned a value at each visit based on the analysis visit windows specified in Section 3.8.2. Missing values will be imputed based on the categorical imputation rules described in Section 3.6.1. The two-sided 95% exact confidence interval based on the Clopper-Pearson method will be provided by HCV genotype (1[1a, 1b, 1 other], 2, and total) for the percentage of subjects with HCV RNA < LLOQ at each visit within each treatment

group and total. The overall category for “HCV RNA < LLOQ” will be divided into the following 2 subcategories: “< LLOQ TND” for subjects with target not detected and “< LLOQ detected” for subjects with < LLOQ in tabular displays.

Graphs for the percentage of subjects with HCV RNA < LLOQ over time during treatment will be displayed by HCV genotype (1[1a, 1b, 1 other], 2, and total).

Summary statistics will be presented for absolute values and change from baseline in HCV RNA (\log_{10} IU/mL) by HCV genotype (1[1a, 1b, 1 other], 2, and total) and visit through EOT.

Imputation rules described in Section 3.6.1 will be used to assign HCV RNA values for missing values at visits that are bracketed by “< LLOQ TND” and/or “< LLOQ detected”. Otherwise, a missing = excluded analysis will be performed. Plots of the mean \pm SD and median (Q1, Q3) of absolute values and changes from baseline in HCV RNA through EOT will be presented by HCV genotype (1[1a, 1b, 1 other], 2, and total).

For the SVR12 endpoint analysis, a summary table of the number and percentage of subjects with SVR12, virologic failure (VF), and Other will be created by HCV genotype (1[1a, 1b, 1 other], 2, and total). All subjects who achieved SVR12 will be categorized as SVR12. Virologic failure will be descriptively summarized as “on-treatment virologic failure” and relapse (which will be broken down by study drug completed yes/no). Subjects who do not achieve SVR12 and do not meet criteria for virologic failure will be categorized as “Other”. The denominator for relapse will be the number of subjects who had HCV RNA < LLOQ on their last observed on-treatment HCV RNA measurement; otherwise, the denominator will be the number of subjects in the FAS.

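### No rule in the public text covers non-study HCV therapy started before the SVR12 or SVR24 sample, and routine medication recording stops at day 30, so a retreated and suppressed failure would count as a responder (low priority)

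*SAP*

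**What the plan says.** **Endpoint.** SAP 6.1.1 gives SVR12 as "defined as HCV RNA < LLOQ (ie, < 15 IU/mL) 12 weeks after cessation of treatment". Protocol 8.5.1 restates it in the same terms. Protocol 8.2 and SAP 3.8.1 tie timing to the last dose of study drugs. SAP 3.6.1 deals with missing values only: bracketing, failure if not bracketed, and SVR24 taken from SVR12 status when no later sample exists.

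**Follow-up.** Subjects stopped for virologic failure complete all posttreatment visits (Protocol 3.4.1). Visits are timed from the last dose "regardless of whether they are a virologic failure or discontinued study drugs early" (Protocol 6.4). The FU-12 window is days 70-146 and the FU-24 window days 147-210 (SAP Table 3-2). The latest HCV RNA record in each window is used (SAP 3.8.3).

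**Classification.** SAP 6.2.2: "All subjects who achieved SVR12 will be categorized as SVR12". Only subjects without SVR12 can be shown as virologic failure or Other. Relapse under SAP 6.2.1 must be "confirmed by 2 consecutive values or last available posttreatment measurement". Mandatory confirmation, "no later than 2 weeks after an initial observation indicating virologic failure during the on-treatment phase", does not extend to follow-up (Protocol 3.4.1).

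**Medication recording.** Protocol 5.6 asks for medications "up to and including 30 days after the last dose of study drugs need to be recorded in the source documents and eCRFs". Appendix 2, footnote f, agrees: "Adverse events and Concomitant Medications will be collected up to 30 days after the last dose of all study drugs". The posttreatment Week 12 and Week 24 visit lists (6.4.2, 6.4.3) have no medication check. Two exceptions reach past day 30. At an unscheduled visit the investigator "should, at a minimum, collect AE and concomitant medication information" (6.6), and drugs used to treat an SAE are recorded (7.3). SAP 7.4 lists all recorded medications but leaves those started after the last study dose out of the summary table.

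**The concern.** SVR12 is meant to credit study drug with a cure. Under these rules the HCV RNA value counts whatever produced it. There are three routes to a false success:

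- A subject with confirmed on-treatment failure starts another regimen and is below LLOQ at FU-12. The separate virologic-failure criteria are met, but the outcome table shows SVR12.
- A subject has one value at or above LLOQ at FU-4, starts another regimen and is below LLOQ at FU-12. The single value is neither confirmed nor last, so relapse is not met at all.
- A subject fails at FU-12, is retreated and is below LLOQ at FU-24. This counts as SVR24.

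The error runs in one direction only. There is no between-arm test (SAP 3.5) and genotype 2 is descriptive, so each arm is read from its own rate, interval and failure count. Those are the figures affected. Therapy begun in days 1-30 would be recorded, but no endpoint rule uses it. Therapy begun later would usually not be recorded, so an analyst could not rule the error out.

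**Working it through.** **1. The plan's own figure.** Inputs (Protocol 8.8, SAP 1.3): n = 45 genotype 1 subjects per arm, null 50%, alternative 50 + 27 = 77%, two-sided exact test at 0.025.

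- Critical count: the smallest r with 2·P(X ≥ r | 45, 0.5) ≤ 0.025. At r = 30 this is 2 × 0.01785 = 0.0357; at r = 31 it is 2 × 0.00805 = 0.0161. So r = 31.
- Power: P(X ≥ 31 | 45, 0.77) = 0.925. The stated power of over 90% reproduces.

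**2. Effect of one case.** 1/45 = 2.2 points in a genotype 1 arm; 1/10 = 10 points in a genotype 2 arm of about 10. Clopper-Pearson 95% intervals:

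- 34/45 = 75.6% (60.5-87.1) becomes 35/45 = 77.8% (62.9-88.8).
- With two cases, 40/45 = 88.9% (75.9-96.3) becomes 42/45 = 93.3% (81.7-98.6).

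**3. Effect on the test.** With k misclassified subjects, 31 − k true responders suffice. One case changes the result only at 31/45 (p = 0.016) versus 30/45 (p = 0.036). An observed 35/45 (p = 0.00025) needs five false successes to fall to 30 true responders, which is 5 of 15 true failures (33%).

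**4. Effect on the estimate, by assumption.** The documents give no retreatment rate. Let d be the share of failures detectable early enough to be retreated before the sample, and f the share of those who are retreated and below LLOQ at FU-12. At a true SVR12 of 77%, 45 × 0.23 = 10.35 failures are expected, and the rise in points is 100 × 10.35 × d × f / 45 = 23·d·f.

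For d, the protocol's own data (other populations and regimens) give 2 of 6 non-responders as relapses seen by posttreatment Week 4 (1.2.3.1.4) and 4 of 8 (SOF+RBV arm, 1.2.3.2.4), that is 33% to 50%. Taking d = 1 gives an upper illustration only.

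| f | d = 1/3 | d = 1/2 | d = 1 (upper illustration) |
|---|---|---|---|
| 0% | 0 | 0 | 0 |
| 5% | 0.4 | 0.6 | 1.2 |
| 10% | 0.8 | 1.2 | 2.3 |
| 20% | 1.5 | 2.3 | 4.6 |

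On the same basis, the five cases in step 3 would be 5 of 5 to 5 of 7.5 detectable failures, or 67% to 100%.

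**5. Chance of declaring success in one arm.** This is P(X ≥ 31) at a recorded rate of p + (1 − p)·d·f. At a true 50% it is 0.008, 0.019, 0.041 and 0.143 for d·f = 0, 5%, 10% and 20%, against a nominal upper tail of 0.0125. At a true 90% it is about 1.00 throughout.

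**6. Unrecorded start dates that matter.** The FU-12 visit is at 84 ± 5, days 79-89. Time to suppression is an assumption. Protocol 1.2.3.1.4 reports over 88.5% below LLOQ at Week 4, in another population.

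- Needing 28 days: latest start is day 51-61, so 21 to 31 days after day 30.
- Needing 14 days: latest start is day 65-75, so 35 to 45 days.

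A later unscheduled sample, up to day 146, would lengthen both. For FU-24 (168 ± 5, days 163-173) with 28 days, the latest start is day 135-145, so 105 to 115 days.

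**The case against.** **The endpoint section is not in the public text.** Protocol 8.1.1, 8.1.2 and 3.5 are missing from it, and the eCRF is not included. A reader might infer that the plan certainly has no such rule. That cannot be shown. The legible restatements in Protocol 8.5.1 and SAP 6.1.1 carry none, and nor do SAP 3.6.1, 3.8.3 or 6.2.2. The point is limited to that text.

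**Retreatment is unlikely.** Protocol 1.1, 1.4 and 1.5 say no approved therapy exists after DAA failure. This stands and is the main reason for low priority. A reader might take the 71% SVR12 on LDV/SOF retreatment in Protocol 1.4 as a sign that retreatment is to be expected here. It is a cited result in other patients and says nothing about subjects starting a new regimen within weeks of failing this study.

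**Most failures are not exposed.** Missing-data failures have no suppressed FU-12 value, and relapses first seen at the FU-12 sample cannot have been treated before it. This stands. For SVR12 the exposure is mainly on-treatment failures and relapses seen by FU-4, plus later unscheduled samples in the window.

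**Safeguards exist.** Days 1-30 are recorded and listed, unscheduled visits collect medications, and Protocol 9.1.5 asks for medication dates in source notes. The by-visit tables (SAP 6.2.2) would show a value at or above LLOQ at FU-4, and a reversal could be queried. These help with detection, but none changes the scoring, and viral results do not show whether or when another drug began. The two-value relapse rule is an ordinary guard against a spurious result and is not itself at fault.

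**Conclusion.** The point holds for the public text, at low priority. A failure who is retreated and suppressed would be scored SVR12 or SVR24, and therapy begun after day 30 would go unrecorded outside unscheduled visits and SAE treatment. The bias is favourable, at 2.2 points per case in genotype 1 and about 10 in genotype 2. At a true 77% the illustrated rise in SVR12 is 0 to 2.3 points if a third to a half of failures are detectable in time; 4.6 points is an upper illustration. These figures rest on assumed retreatment shares and on detectability borrowed from other populations. SVR24 has the longer exposed interval.

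A reader might infer that the primary test is unsound. The documents do not support that. The design reproduces (31/45, 92.5% power), one case matters only at the boundary, and if true SVR12 is well above 50% the result does not change. What is affected is the estimate, its interval and the failure counts.

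**What to change.** 1. **Recording** (Protocol 5.6, 6.4.2, 6.4.3, Appendix 2): record any non-study HCV antiviral and its start date through posttreatment Week 24.
2. **Scoring** (SAP 3.6.1, 3.8.3, 6.1.1), for subjects with such recorded therapy, in this order:
   - (a) exclude HCV RNA collected after its start from record selection and bracketing;
   - (b) if a valid value from before the start remains in the FU-12 (or FU-24) window, use it;
   - (c) otherwise score the subject as not SVR12 (or not SVR24), without carrying SVR12 forward to SVR24.
3. **Classification** (SAP 6.2.1, 6.2.2), same subjects only: apply the virologic-failure definitions to values from before the start, and place those who are not SVR12 under virologic failure or Other. All other subjects are handled as now, so the outcome table and the primary endpoint keep one numerator.

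If Protocol 8.1.1, 8.1.2 or 3.5 already holds such a rule, the SAP need only state it, and the recording period should match.

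Cost: one eCRF item at two visits already scheduled, a short SAP rule, and a protocol modification with IRB/IEC approval (Protocol 9.2.1). SVR12 may come out slightly lower. The critical count and power do not change. This is a recording and analysis rule only and proposes no clinical management.
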